## 5. DEFINITIONS

### 5.1 Time-Related Terms

#### 5.1.1 Baseline Visit

The *Baseline visit* is on the day before or on the day of study cardiac surgery prior to start of surgery (whichever comes last).

#### 5.1.2 Study Day

The *study day* describes the relative day of an observation starting with the first study transfusion date designated as Study day 1. It will be calculated as:

- For days prior to the first study transfusion date, Study Day = Date – Date of first study Transfusion
- For days on/after the first study transfusion date, Study Day = Date – Date of first study Transfusion + 1

#### 5.1.3 RBC Exposure

The *extent of exposure* to RBC transfusions will be assessed by units and volume of treatment exposure, derived as:

- Units of treatment exposure = RBC Units transfused from surgery till both 48 hours post-surgery and ATSP
- Volume of treatment exposure = RBC volume transfused from surgery till both 48 hours post-surgery and ATSP
- For the purposes of the statistical analysis plan,  $\geq 4$  Total RBC units related to an 8-hour surgery and  $\geq 10$  units of RBCs within 24 hours represents larger volume or massive transfusion, respectively.

### 5.2 Efficacy Related Definitions

#### 5.2.1 Baseline Score

The *baseline score* is the last measurement taken before the first study RBC transfusion and before the start of the study cardiac surgery.

### **5.2.2 Change and Percent Change from Baseline**

The change and the percent change from baseline in a measure at a post-baseline visit will be derived as:

- Change = (Score at the Post-Baseline Visit) – (Baseline Score).

If there are multiple measurements at a post-baseline visit, the maximum value will be used.

For the analysis of primary efficacy endpoint, maximum serum creatinine within  $48 \pm 4$  hours post-surgery will be used.

## **5.3 Other Definitions**

### **5.3.1 Prior and Concomitant Medications**

Medications will be categorized into prior medications and concomitant medications which coded using WHO Drug Global B3, March 2018. Specifically, prior medication is defined as any medication taken and ended prior to the study RBC start date. Concomitant medication is defined as any medication taken concurrently while receiving study RBC, i.e., the treatment period (period of time from first unit to last unit) of a concomitant medication taken by a subject must overlap with the treatment period.

### **5.3.2 Non-Study RBC**

In this study, non-study RBC (conventional RBC) may be transfused according to the protocol to provide the patient with an appropriate and necessary treatment when study RBCs are unavailable or patient's need for RBC transfusions exceeds the quantity of study RBCs in inventory at the hospital blood bank (e.g., during a Massive Transfusion Protocol). Unlike Test and Control RBCs, conventional RBCs may be sourced from any blood collection center and are not manufactured using study RBC production protocols. The use of cell saver blood is not included as part of non-study RBCs.

The non-study RBC use will be summarized for Test and Control in terms of units and proportions for both within 48 hours and whole ATSP.

## 6. STUDY POPULATION

### 6.1 All Enrolled Patients Set (ALL)

The ALL set includes all subjects who signed informed consent and were randomized.

### 6.2 Modified Intent-to-Treat (mITT) Population

The mITT includes all randomized subjects who received at least one study transfusion. Efficacy analyses will be performed using the mITT and summarized by assigned treatment as randomized. Safety analyses will be performed using the mITT and summarized by actual treatment received.

### 6.3 Per-Protocol Set (PPS)

The PPS is a subset of the mITT. It will be the analysis population for exploratory and sensitivity analyses and will be summarized using treatment as randomized. Any subject affected by an important protocol deviation that might affect the primary efficacy analysis will be excluded from the PPS. The PPS will be identified before the unblinding of treatment assignments.

Before the database lock and before unblinding the treatment assignments, Cerus' study team will review all protocol deviations, identify subjects with any protocol deviation that could impact the efficacy outcome, and determine whether or not to exclude the subject from the PPS.

The following protocol deviations may be considered as important and will lead to an exclusion of subjects from the PPS:

- Randomized to Test but received Control treatment within 48 hours of the end of surgery.
- Randomized to Control but received Test treatment within 48 hours of the end of surgery.
- Subjects who received non study RBC transfusions within 48 hours completion of surgery due to a blood bank error when appropriate study RBC components were available.
- Subjects who did not receive any study RBCs within 48 hours of the end of surgery.
- Subjects who received a study RBC transfusion but have no assessment of sCr concentrations after the transfusion and within  $48 \pm 4$  hours of the end of surgery.

Additional protocol deviations may be considered important at the blinded data review meeting and will be documented appropriately. If a subject is randomized incorrectly or is administered the incorrect study treatment, analyses of the efficacy endpoints will be based on the assigned treatment, whereas all other analyses will be based on the actual treatment received.

Note that the study protocol allows for the transfusion of non-study RBCs when study RBCs are unavailable or the patient's need for RBC transfusions exceeds the quantity of study RBCs in

inventory at the hospital blood bank (e.g., during a Massive Transfusion Protocol). These non-study RBC components are therefore considered to be transfused per protocol.

#### **6.4 Study RBC Only Set (SROS)**

The SROS is a subset of the PPS. Subjects who received non study RBC within 48 hours of the completion of study surgery will be excluded from the SROS. It will be the analysis population for the exploratory analysis with sensitivity analyses and will be summarized using treatment as randomized.

### **7. GENERAL CONSIDERATIONS**

All measures will be summarized by treatment (planned or actual received) descriptively. Continuous variables will be summarized using descriptive statistics such as number of observations (n), mean, standard deviation, median, minimum, and maximum. Categorical variables will be tabulated using frequency (n) and percent (%).

The statistical testing will be conducted at a significance level of 0.05 (two-sided) and the 95% confidence interval will be shown, unless specified otherwise. No statistical testing will be conducted for safety measures.

All data manipulations, descriptive summaries, and statistical hypothesis testing will be performed using Statistical Analysis System (SAS) Version 9.4 or later.

#### **7.1 Handling of Missing Data**

##### **7.1.1 Efficacy Measure**

For the primary analysis of serum creatinine (sCr) increase within 48 hours of surgery start, no imputation is needed for the analysis on observed cases using the Miettinen and Nurminen (M&N). In this case, the maximum observed post-baseline sCr value will be used to calculate the increase from baseline. If a subject has no post-baseline sCr within  $48 \pm 4$  hours post-surgery at all, this subject will be treated as missing the primary endpoint. These missing values will be imputed via multiple imputation in the sensitivity analysis with logistic regression approach.

In the sensitivity analysis with Pattern-Mixture Model (PMM) approach, for subjects who received non-study RBC within 48 hours post-procedure, any sCr values collected after the transfusion of non-study RBC will be censored (i.e., treated as missing). Missing sCr data will be imputed using the Multiple Imputations (MI) approach.

Missing secondary efficacy endpoints will not be imputed.

##### **7.1.2 Safety Measures**

Descriptive summaries of safety measures will be based on observed data only. No imputation of missing scores will be implemented.

### 7.1.3 Dates for Medical Events and Medications

Completely or partially missing onset and resolution dates of medical history (MH), AE, and concomitant medications (CM) will be imputed as follows:

**Table 2: Handling of Missing Data for Medical Events and Medications**

Date	Type of Missing Date	Handling of Missing Date
Event onset date (e.g., YYYY-MM-DD)	Completely missing	No imputation will be applied: For AE, the event will be considered treatment emergent. For CM, the event will be considered concomitant. For MH, the event will be considered to occur prior to Inform Consent date.
	Only YYYY is available	Use the first day of YYYY (Jan. 1 st ) to impute the missing month and date parts of the onset date.
	YYYY and MM are available, but DD is missing	Use the first day of MM (1st) to impute the missing date part of the onset date.
Event resolution date (e.g., YYYY-MM-DD)	Completely missing	No imputation will be applied. The event will be considered ongoing (i.e., not resolved) at the last visit date.
	Only YYYY is available	Use the last day of YYYY to impute the missing month and date parts of the resolution date.
	YYYY and MM are available, but DD is missing	Use the last day of MM to impute the missing date part of the resolution date.

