#### 3.2.3 Safety Endpoints

The primary safety endpoints are:

- Proportion of patients with any treatment-emergent adverse events (TEAEs) possibly, probably, or definitely related to study RBC transfusion through 28 days after the last study transfusion.
- Proportion of patients with treatment emergent (TE) antibodies with confirmed specificity to INTERCEPT RBCs by end of study (i.e.,  $75\pm15$  days after the last study transfusion).

Additional safety assessments will include:

- Treatment-emergent AEs through 28 days after the last study transfusion.
- Treatment-emergent SAEs through 28 days after the last study transfusion.
- Transfusion reactions (as defined by the CDC National Healthcare Safety Network [NHSN] Hemovigilance Module protocol) through 28 days after last study transfusion.
- Treatment-emergent immunization to RBC alloantigens through  $28\pm3$  days after the last study transfusion.
- Treatment-emergent immunization to HLA alloantigens through  $28\pm3$  days after the last study transfusion.

Please note no formal hypotheses will be tested on the primary safety endpoints.

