INTERCEPT RBC antibody screen (S-303-specific antibody screen)	X			X 	X 	X		X
Sample for HLA antibodies	X					X		
All other blood components (including non- study RBCs) transfused, if any				X	X	X		
Estimated blood loss from surgery				X				
Estimated blood loss from other source including chest tube(s)					X 			
AEs/SAEs/TRs	X*	X*	X*	X*, 		X ^		
Documentation of vital status and need for RRT						X	X 	X

1. For Screening/Randomization purposes, data from medical records within 30 days prior to their surgical procedure may be used.
2. See protocol Table 7.2: Hematology and Chemistry Testing for details on required labs.
3. These assessments can be combined with screening assessments if screening visit is also on Day -1 or Day 0 Pre-Surgery.
4. Data collected on eCRFs only as available from medical records if performed as Standard of Care.
5. Hemodynamic Parameters: Peripheral O2 Saturation, Mean Arterial Pressure, Central Venous Pressure.
6. These assessments are required to be collected daily on Day 1 through Day 7 post surgery or until discharge. If subject returns after discharge for a postoperative standard of care visit, assessments will be collected in eCRFs on the appropriate study day.
7. Any drugs given to induce anesthesia or drugs given as a prophylactic in combination with anesthesia prior to surgery do not need to be recorded. Medications given during anesthesia to treat an AE/SAE need to be recorded.
8. Urine output data collected daily while a urinary catheter is in place. The date entered should reflect the start of the collection and match the visit date.
9. S-303 screen must be performed whenever a routine RBC alloantibody screen (IAT) is performed during the transfusion period.
10. Laboratory results recorded in the eCRFs during this period will only be those assessed as clinically significant by the Investigator.
11. Assess at Day 30 post surgery via clinic visit, medical record, or phone call. Any RRT that is provided prophylactically during surgery while the subject is on a bypass machine does not meet this endpoint.
12. # Eligible patients will be randomized up to 7 days before or on the day of surgery, but prior to the start of surgery (i.e., induction of anesthesia).
13. \* The adverse event, serious adverse event and transfusion reaction collection period will begin at the start of surgery or the first study RBC transfusion, whichever is first.

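### Partial AE onset dates are imputed to the 1st of the month or 1 January with no floor, so AEs from the transfusion month are usually dated before the first study RBC, while undated AEs count as treatment emergent

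*SAP*

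**What the plan says.** SAP Section 7.1.3 sets one rule for three kinds of record: "Completely or partially missing onset and resolution dates of medical history (MH), AE, and concomitant medications (CM) will be imputed as follows". In Table 2, an onset date with month and year but no day is handled as "Use the first day of MM (1st) to impute the missing date part of the onset date". An onset date with only the year is handled as "Use the first day of YYYY", that is, 1 January. Neither row has a lower limit or an exception for AEs.

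The row for a completely missing onset date goes the other way: "For AE, the event will be considered treatment emergent".

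Three other places matter:
- Section 3.2.3 makes one of the two primary safety endpoints "Proportion of patients with any treatment-emergent adverse events (TEAEs) possibly, probably, or definitely related to study RBC transfusion". The window for this endpoint closes 28 days from the final study RBC.
- The Table 1 footnotes state that "The adverse event, serious adverse event and transfusion reaction collection period will begin at the start of surgery or the first study RBC transfusion". The earlier of the two applies.
- Section 5.1.2 counts study days from the date of the first study transfusion as day 1.

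**The concern.** First-of-period imputation suits medical history and medications, where the earliest possible date is the natural choice. For AEs it produces dates that the SAP itself excludes: an AE in this database should not begin before collection opens, yet the imputed date often does.

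Table 2 is also inconsistent across its rows. With no date at all, the event counts. With the month known to be the month of transfusion, the event is usually dated before treatment. Knowing more about the date makes the event less likely to count.

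The possible error runs one way. AEs are collected from surgery or first study RBC through 28 days after the last study transfusion. Within that window, moving an onset earlier can take a true treatment-emergent event out but cannot validly bring one in. At stake are the TEAE and treatment-emergent SAE summaries and, in some patients, the related-TEAE primary safety endpoint.

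**Working it through.** The SAP gives no figure on this point, so there is none to reproduce. The check applies the Table 2 rule to a calendar.

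**Worked example.** Surgery and first study RBC fall on the 15th. An AE begins later that month and its day is not recorded. Table 2 dates it to the 1st, 14 days before collection opened. Under Section 5.1.2 its study day is 1 − 15 = −14.

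**Inputs from the SAP.** The imputation rules are those of Table 2. The endpoint window ends 28 days after the last study transfusion (Section 3.2.3). Study RBCs may be given up to post-operative Day 7 (Section 4.1). The window measured from the *first* study RBC is therefore 28 days if transfusion is confined to one day, and up to about 7 + 28 = 35 days otherwise.

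**Assumptions.** The first study RBC is equally likely on each of 365 days (7 months of 31 days, 4 of 30, one of 28). True onset is uniform over days 0 to W after it.

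**Formula, day missing.** In a month of L days, with onset k days after the first study RBC, the AE is misdated when the transfusion is not on the 1st and the onset is still in that month. That gives max(L − 1 − k, 0) transfusion dates. Sum over k = 0 to W and over the 12 months, then divide by 365 × (W + 1).

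- W = 7: 8 × (365 − 12) − 12 × 28 = 2488; 2488 / 2920 = **85.2%**.
- W = 28: 31-day months 29 × 30 − 406 = 464; 30-day months 29 × 29 − 406 = 435; February 378. Then 7 × 464 + 4 × 435 + 378 = 5366; 5366 / 10585 = **50.7%**.
- W = 35: 465, 435 and 378. Then 7 × 465 + 4 × 435 + 378 = 5373; 5373 / 13140 = **40.9%**.

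A direct enumeration over the 365 dates of 2022 gives the same values:

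| Window after first study RBC | AE falls in transfusion month | Of those, dated before transfusion | Share of all day-missing AEs misdated |
|---|---|---|---|
| Days 0–7 | 88.5% | 96.3% | 85.2% |
| Days 0–28 | 54.0% | 93.9% | 50.7% |
| Days 0–35 | 43.7% | 93.6% | 40.9% |

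A same-month AE escapes only if the first study RBC was on the 1st (12/365 = 3.3% of dates). An AE from a later month is dated to the 1st of that month, which is after the transfusion, so it is unaffected.

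**Formula, year only.** The share is (364 − W/2) / 365: 360.5/365 = 98.8% for W = 7, 350/365 = 95.9% for W = 28, and 346.5/365 = 94.9% for W = 35.

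**With a floor.** Using the later of the first of the month and the first study RBC date, the enumeration over days 0–28 leaves no day-missing AE dated before the transfusion.

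**From events to the endpoint.** These shares are per partially dated AE. The endpoint counts patients. One patient lost from an arm lowers that arm's rate by 1/146 = 0.7 percentage points at 146 per arm, or 1/200 = 0.5 points at 200 per arm (the sizes in Section 4.3, split equally).

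**The case against.** The strongest objection is that the SAP never says when treatment emergence begins. Section 3.2.3 gives only the end of the window, Section 5.1.2 defines study day and nothing more, and the AE footnote refers to a protocol section that is not at hand. If every collected AE counted as treatment emergent whatever its date, none would drop out. This stands as a limit on certainty. It does not remove the point: under that reading, Table 2 would not need a special rule making undated AEs treatment emergent. That rule implies a date-based definition but does not prove it.

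A reader might infer that the rule simply removes same-month events from the primary safety endpoint. The SAP does not support that. The endpoint is the proportion of patients with any related TEAE, so it changes only if the misdated AE is related and is the patient's only related TEAE. The antibody endpoint is untouched.

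A reader might also infer a bias towards Test. Nothing shows this: the rule is the same in both arms, no formal hypothesis is tested on the primary safety endpoints (Section 3.2.3), and the safety p-values are exploratory (Section 11).

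The high shares also need care. Year-only onset should be very rare in a short, monitored window. The days 0–7 figure covers mostly the hospital stay, when AEs are recorded daily and days are least likely to be missing. Post-discharge events are the more likely source of partial dates, which makes the longer windows the better guide.

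**Conclusion.** The point holds in a conditional form. The misdating itself is certain from Table 2: with no floor, AEs from the transfusion month or year usually receive an onset before the first study RBC and before collection began. Their loss from the TEAE and SAE summaries depends on treatment-emergent status being set by onset date, which is the likely reading. Their effect on the related-TEAE endpoint further requires that no other related TEAE keeps the patient in the count.

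Under uniform onset, about 41–51% of day-missing AEs are misdated for a 28–35 day window after the first study RBC. The number of partial AE dates is not given and is probably small. The expected result is a modest understatement of AE incidence in both arms. It is no threat to the efficacy conclusion and is not evidence of a distorted comparison. The correction is still worth making, because the stated rule gives a wrong answer and contradicts the SAP's own default for missing dates.

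**What to change.** In Table 2, add a separate rule for AE onset:
- If the known month and year (or the known year alone) equal those of the first study RBC, impute the date of the first study RBC, unless the resolution date or other recorded data show that the AE ended or began before it.
- If the known part is later, use the first day of that period.
- Leave the completely missing row, and the medical history and medication rules, unchanged.

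The cost is a few lines of Table 2 and of code. The downside is that collection can open at the start of surgery, before any study RBC. A few AEs that began in surgery before the first study RBC may therefore be counted as treatment emergent, and TEAE counts may rise slightly. That error is conservative and matches how the SAP already treats an AE with no date.

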### 7.2 Multi-Center Studies

This is a multi-center study enrolling subjects from approximately 15-20 U.S sites. The number of subjects per site might be small. Separate analyses by site are not meaningful and not desirable. Therefore, there are no analyses adjusting for sites. All subjects from all sites will be pooled for statistical analysis.

### 7.3 Multiple Comparisons / Multiplicity

No multiplicity adjustment is needed for this study. The superiority of the primary efficacy endpoint will be tested only after the non-inferiority is met.

### 7.4 Interim Analysis

A blinded interim analysis was performed to re-estimate the sample size in October 2021 which resulted in the reduction in sample size from 600 to  $\geq 292$ . This blinded interim analysis was discussed with the FDA on October 6, 2021, in Q-Sub BQ150260/6.

No other interim analysis is planned for this study.

## **8. DATA SAFETY AND MONITORING BOARD**

The study data and safety will be monitored on a regular basis by the Data and Safety Monitoring Board (DSMB) to ensure patient safety and review protocol compliance. The DSMB will review group-blinded data generated by an independent statistician. All DSMB members are independent of the sponsor.

## **9. SUMMARY OF STUDY POPULATION DATA**

### **9.1 Subject Disposition**

The disposition of ALL (i.e., all randomized subjects) will be summarized by treatment and overall. The summary will include the number and percentage of ALL subjects in the mITT, PPS and SROS. The disposition summary will also include the number and percentage of completers and non-completers, as well as the number and percentage of discontinuations of the study and of the study RBC by the primary discontinuation reason.

### **9.2 Demographics and Baseline Characteristics**

Subject demographics and baseline characteristics will be descriptively summarized for the mITT population by planned treatment and overall. Specifically, for subject demographics, the following variables will be summarized:

- Age at randomization (continuous and categorical: < 65 years or  $\geq$  65 years)
- Sex (categorical: Male or Female)
- Ethnicity (categorical: Hispanic/Latino or Not)
- Race (categorical: American Indian or Alaska Native, Asian, Black, Native Hawaiian or Pacific Islander, White, or Other)

For baseline characteristics, the following variables will be summarized:

- Trust Score
- Serum Creatinine (continuous and categorical: < 1.2 or  $\geq$  1.2 mg/dL)
- Blood Type (A, B, O and AB)
- RH factor (Positive or Negative)

### **9.3 Medical, Surgical and Transfusion History**

For this study, medical history and adverse events will be coded using MedDRA 21.1, 2018. Each medical event will be classified into a SOC and mapped to a Preferred Term (PT).

The medical and surgical history will be summarized for the mITT. Subjects reporting any medical and surgical history at baseline will be tabulated by SOC and PT for each planned treatment and overall.

